6.1 Safety Analysis Set

The safety analysis set will consist of all study subjects who are randomized and receive at least one dose of AMG 890 or placebo.

Subjects withdrawing prior to any AMG 890 or placebo administration due to adverse events related to study procedure will not be included in the safety analysis set but those adverse events will be listed.

6.2 Pharmacokinetic/Pharmacodynamic Analyses Sets

6.2.1 Pharmacokinetic (PK) Analysis Set

The PK analysis set will consist of all dosed subjects for whom at least one PK parameter or endpoint can be reliably estimated.

6.2.2 Pharmacodynamics (PD) Analysis Set

The PD analysis set will consist of all dosed subjects for whom at least one PD parameter (**Lp(a)**) has a baseline value and at least 1 post-baseline measurement available. **Baseline values for Lp(a) are defined as the mean of screening and day 1 predose. If for any reason only 1 value is available, then that value will be used as baseline.**

7. Planned Analyses

7.1 Interim Analysis and Early Stopping Guidelines

No interim analysis is planned for this study. However, the study will have Dose Level Review Meetings (DLRMs) during the study for each cohort.

All relevant study data, including demographics, investigational product administration, medical history, concomitant medications, adverse events, electrocardiogram (ECG), vital signs, and laboratory results will be reviewed. Data will be subject to ongoing checks for integrity, completeness, and accuracy in accordance with the Data Management Plan; however, there is no requirement to resolve outstanding data queries ahead of the snapshot. All available data up to and including the data cut-off date will be included in the analysis based on an “as-is” snapshot of the database without data locking.

For cohorts 1 to 5, and cohort 9, escalation to a higher dose cohort will only proceed when the previous dose regimen has been found to be safe and reasonably tolerated based on available safety data through study day 15 for all subjects and upon unanimous recommendation of the DLRT. Available data from previous cohorts will also be considered. The next cohort will be open for enrollment immediately following the DLRT recommendation and Amgen decision.

Enrollment into cohorts 6 to 8 will be initiated after cohort 4 dose level has been found by the DLRT to be safe and reasonably tolerated based on available safety data through study day 15. Cohorts 5, 6 and 7 may be enrolled in parallel. For cohorts 6 and 7 eligible subjects will be first enrolled into cohort 6 and then into cohort 7. Cohort 8 will be enrolled after implementation of protocol amendment 5 . Enrollment into cohort 9 can be initiated after the preceding dose regimen has been found by DLRT to be safe and reasonably tolerated based on available safety data through at least study day 15 of cohort 5.

7.2 Primary Analysis

The primary analysis will occur after all subjects have completed the end of treatment

visit. At the primary analysis, the primary, secondary, and exploratory endpoints (if applicable) will be analyzed. All data up to each subject's end of treatment visit will be included in the primary analysis.

7.3 Final Analysis

The final analysis will occur after all subjects have completed the study. The follow-up time points will be summarized at the final analysis. The final analysis and primary analysis may be combined if they are scheduled to occur at similar times.

Data will be subject to ongoing checks for integrity, completeness and accuracy in accordance with the Data Management Plan with the expectation that all outstanding data issues are resolved ahead of the final database lock.

8. Data Screening and Acceptance

8.1 General Principles

The objective of the data screening is to assess the quantity, quality, and statistical characteristics of the data relative to the requirements of the planned analyses.

8.2 Data Handling and Electronic Transfer of Data

The Amgen Global Study Operations-Data Management (GSO-DM) department will provide all data to be used in the planned analyses. This study will use the RAVE database.

The final analysis specified in this statistical analysis plan will be performed once all subjects have completed the study and the database is locked post the clean snapshot.

Analyses supporting DLRMs will be performed on an ongoing basis throughout the study.

8.3 Handling of Missing and Incomplete Data

The frequency of missing and incomplete data is expected to be low in this study and therefore, missing data will not be imputed.

Laboratory measurements that are below the quantification limits will be considered equal to the lower limit of quantification for the calculation of population averages as a part of the summary tables. Clinical lab values below LLQ will not be imputed for individual subject level data in line listings.

Biomarker data that are below the quantification limits will be considered equal to half of the lower limit of quantification for all analyses unless specified otherwise.

PK concentrations that are below the quantification limits will be set to zero when using non-compartmental methods to compute PK parameters.

For partial dates (such as treatment emergent AE, concomitant medication, drug administration etc.) imputation of dates will be carried out as per Appendix A.

8.4 Detection of Bias

Any source that may introduce bias in the analysis e.g. important protocol deviations, imbalance in baseline characteristics among treatment groups, subject dropout for study or treatment related reasons, nonrandom or informative censoring will be noted in the clinical study report.

8.5 Outliers

Any questionable or outliers will be confirmed with GSO DM. In addition, outliers may be identified via the use of descriptive statistics. All confirmed outlier data will be included in the analyses presented in this statistical analysis plan unless there is sufficient scientific justification to exclude them. Any outliers exclude from the analysis will be discussed in the clinical study report (CSR) including the reasons for exclusion and the impact of their exclusion on the study.

Pharmacokinetic (PK) Serum concentration data will be evaluated for outliers by visual inspection, and decisions to re-assay individual samples will be made in accordance with standard pharmacokinetic evaluation practice.

8.6 Distributional Characteristics

Where appropriate, the assumptions underlying the proposed statistical methodologies will be assessed. Data distribution will be explored, if required, data transformations or alternative non-parametric methods of analyses will be utilized.

8.7 Validation of Statistical Analyses

Programs will be developed and maintained and output will be verified in accordance with current risk-based quality control procedures.

Tables, figures, and listings will be produced with validated standard macro programs where standard macros can produce the specified outputs.

The production environment for statistical analyses consists of Amgen-supported versions of statistical analysis software; which is the SAS System version 9.4 or higher.

9. Statistical Methods of Analysis

9.1 General Considerations

Descriptive statistics will be provided for selected demographics, adverse events, vital signs, ECG and selected laboratory measurements. Descriptive statistics on continuous measurements will include means, medians, standard deviations, and ranges, while categorical data will be summarized using frequency counts and percentages. Data will be presented and summarized by treatment group and cohort at each scheduled time point. Graphical summaries of the data may also be presented.

Data for subjects receiving placebo will be combined across cohorts 1 to 5 and separately across cohorts 6 to 9.

When data are summarized by time, the values recorded against the scheduled time points listed in the protocol will be used. When assessing minimum/maximum increases or decreases over the study, all assessments, including unscheduled assessments will be used. Unless stated otherwise in the statistical analysis plan, the data analysis will be conducted using subjects in the safety analysis set. For statistical analyses comparing change from baseline, only subjects with both baseline and at least one post-baseline assessment will be included.

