**Study Design:**

This is a randomized, double-blind, placebo-controlled, single ascending dose (SAD) study in subjects with elevated plasma Lp(a), which will be conducted at 3 to 10 sites in the United States and Australia. Additional sites and countries may be added.

Approximately █ subjects will enroll in 9 SAD cohorts. As described in [Table 1](#) below, for each cohort, subjects will be randomized to receive AMG 890 or placebo SC in a 3:1 ratio. As of Amendment 6, enrollment in cohorts 1 to 8 is closed. There were no safety concerns noted that would preclude enrollment into the higher dose cohorts 8 and 9.

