#### **Summary of Subject Eligibility Criteria:**

Eligibility criteria include:

Across all study cohorts, women of non-reproductive potential and men, both with age between 18 and 60 years, inclusive, for cohorts 1 to 5; with age between 18 and 65 years, inclusive, for cohorts 6 to 8; and with age between 18 and 70 years, inclusive, for cohort 9. Subjects without any clinically significant abnormality in medical history at the time of randomization.

For cohorts 1 to 5, plasma Lp(a)  $\geq$  70 nmol/L and  $\leq$  199 nmol/L, at screening

For cohorts 6 to 9, plasma Lp(a)  $\geq$  200 nmol/L, at screening; for cohorts 6 to 9, at least 6 subjects in each cohort must be on a stable dose of statin for at least 6 weeks at the time of enrollment

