**Investigational Product:**

**Amgen Investigational Product Dosage and Administration:**

A total of █ subjects will be randomized to receive AMG 890 or equal volume of placebo by SC injection as a single dose. The planned doses for AMG 890 are as follows: single SC doses of 3 mg, 9 mg, 30 mg, 75 mg, 225 mg, and 675 mg.

The planned dose escalation schedule may be modified based on treatment-emergent data (safety and/or PD). Dose adjustments (if any) will be made by Amgen on a treatment cohort and not on an individual basis. Each of cohorts 1 to 5 may be expanded up to █ subjects, while applying the same eligibility criteria and the 3:1 AMG 890 to placebo randomization ratio.

**Control Group:** The control group will be those subjects who will be administered placebo. Within each cohort, 2 subjects (or 3 subjects if a cohort consists of █ subjects) will receive an equal volume of placebo.

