**Statistical Considerations:**

Descriptive statistics will be provided for selected demographics, safety, PK, and PD data. Data for subjects receiving placebo will be combined across all cohorts. Descriptive statistics on continuous measurements will include means, medians, standard deviations, and ranges, while categorical data will be summarized using frequency counts and percentages. Data will be summarized by treatment group and at each time point when samples are collected.

[figure not shown]
The number and percent of subjects reporting any treatment-emergent adverse events will be tabulated by system organ class and preferred term and will be further classified by relationship to treatment.

For a full description of statistical analysis methods, please refer to Section [13](#).

**Sponsor:** Amgen Inc.

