### 7.1 Inclusion Criteria

A subject that has provided written informed consent may be eligible for inclusion in this study only if the following criteria are met:

- 101 Men and women with ages between 18 and 60 years old, inclusive, for cohorts 1 to 5; and with ages between 18 and 65 years old, inclusive, for cohorts 6 to **8**; **and with ages 18 and 70 years old, inclusive, for cohort 9**.
- 102 Plasma Lp(a):
  - $\geq 70$  nmol/L and  $\leq 199$  nmol/L for cohorts 1 to 5
  - $\geq 200$  nmol/L for cohorts 6 to 9
- 103 For cohorts 6 to 9, subjects who are on statin must be on a stable dose of the same statin for at least 6 weeks prior to enrollment, and plan to remain on a stable dose (ie, no change in medication or dosage) for the duration of the study
- 104 Body mass index (BMI)  $\geq 18$  and  $\leq 32$  kg/m^2, at screening, **for cohorts 1 to 8**; **BMI  $\geq 18$  and  $\leq 40$  kg/m^2, at screening, for cohort 9**.

105 Women must be of non-reproductive potential:

- Postmenopausal defined as:
  - Age  $\geq$  55 years with cessation of menses for 12 months or more, OR
  - Age  $<$  55 years and no spontaneous menses for at least 12 months, AND with a follicle-stimulating hormone level  $>$  40 IU/L or according to the definition of “postmenopausal range” for the laboratory involved, OR
- History of hysterectomy, OR
- History of bilateral oophorectomy

106 Men must agree to practice an acceptable method of effective birth control while on study or for 90 days after receiving investigational product (for subjects who withdraw prior to end of study). Acceptable methods of effective birth control include sexual abstinence; vasectomy; or a condom with spermicide (men) in combination with barrier methods (diaphragm, cervical cap or cervical sponge), hormonal birth control or IUD (female partner of male participant)

107 Men must be willing to abstain from sperm donation while on study or for 90 days after receiving investigational product (for subjects who withdraw prior to end of study)

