- **For cohort 9, diagnosis of diabetes is not excluded provided diabetes is well-controlled according to treating physician's assessment and discretion, and the subject is on stable doses of diabetes medications for at least 6 weeks prior to enrollment**

206 Planned elective surgery to occur at any time from screening visit through the end of treatment visit for cohorts 1 to 7, and through the end of study visit for cohorts 8 and 9

207 Estimated glomerular filtration rate (eGFR)  $\leq$  60 mL/min/1.73 m^2, as defined by the local laboratory, at screening

208 Triglycerides  $\geq$  5.65 mmol/L (ie, 500 mg/dL) at screening

209 History or clinical evidence of liver dysfunction, including total bilirubin  $>$  upper limit of normal (ULN) or ALT or AST  $>$  1.1 ULN of the laboratory's reference at screening or at day -1 for cohorts 1 to 5, or day -3 to -1 for subjects not on statin in cohorts 6 to 9. For subjects on stable dose of statin in cohorts 6 to 9, ALT or AST  $>$  1.5 ULN of the laboratory's reference at screening or at day -3 to -1.

210 History or clinical evidence of bleeding diathesis or any coagulation disorder, including prothrombin time (PT), activated partial thromboplastin time (aPTT), thrombin time (TT), or platelet count outside of the laboratory's normal reference range at screening

211 **For cohorts 1 to 8, history or clinical evidence of diabetes mellitus, including a fasting glucose  $\geq$  125 mg/dL (6.9 mmol/L) at screening**

212 History or clinical evidence of peripheral neuropathy

213 History of malignancy of any type, other than in situ cervical cancer or surgically excised non-melanomatous skin cancers occurring more than 5 years prior to randomization

214 Positive results for human immunodeficiency virus (HIV) antibodies, hepatitis B surface antigen (HBsAg), hepatitis B core antibody (HBcAb), or hepatitis C virus

ribonucleic acid (RNA). For hepatitis C, hepatitis C antibody (HepCAb) testing is done at screening, followed by hepatitis C virus RNA by polymerase chain reaction (PCR) if hepatitis C antibody is positive.

215 Subject was previously enrolled in this study or has been previously exposed to AMG 890

216 Use of any herbal medicines, vitamins or supplements known to affect lipid metabolism (eg, fish oils > 4000 mg/day, red yeast rice extract), within 30 days prior to dosing on day 1

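### The cohort 6 to 9 placebo pool mixes 225-day and 365-day adverse event windows, so crude TEAE incidence will tend to look worse for cohorts 8 and 9 than for placebo even with no drug effect

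*SAP*

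**What the plan says.** **Pooling.** SAP 9.1 and Protocol 13.5.1 use the same sentence: "Data for subjects receiving placebo will be combined across cohorts 1 to 5 and separately across cohorts 6 to 9". The protocol synopsis, under Statistical Considerations, says instead: "Data for subjects receiving placebo will be combined across all cohorts".

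**Counts.** In each cohort "subjects will be randomized to receive AMG 890 or placebo SC in a 3:1 ratio". Table 1, in both documents, plans 3 placebo subjects in each of cohorts 6 and 7 and 2 in each of the others.

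**Windows.** The end of treatment visit is day 225 for cohorts 6 and 7 and day 365 for cohorts 8 and 9 (Protocol synopsis, End of Treatment; SAP 5). SAP 5 counts TEAEs to each subject's own end of treatment date, or to study exit for those who leave early. SAP 7.2 cuts the primary analysis at the same visit.

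**Summaries.** SAP 9.6.1 gives subject incidence by treatment group and cohort over the treatment period. It names no common cut-off and no exposure adjustment. SAP 9.6.2 summarizes laboratory values by scheduled time point and allows optional shift tables to the maximum and minimum post-baseline value.

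**Eligibility.** The age limits are "with age between 18 and 65 years, inclusive, for cohorts 6 to 8" but "and with age between 18 and 70 years, inclusive, for cohort 9". Protocol 7.1 caps BMI at 32 kg/m² for cohorts 1 to 8 and at 40 for cohort 9. Protocol 7.2 excludes diabetes in cohorts 1 to 8, whereas "For cohort 9, diagnosis of diabetes is not excluded provided diabetes is well-controlled" on stable medication.

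**The concern.** TEAE incidence is a primary endpoint, and the placebo pool is the only reference shown beside each active cohort. Crude incidence rises with time observed. Among subjects with Lp(a) of 200 nmol/L or more, the two lower doses (9 and 75 mg) have the short window and the two higher doses (225 and 675 mg) the long one. Window length therefore tracks dose, and a pool that mixes both windows sits between them. With no drug effect, the tables could show TEAEs rising with dose and exceeding placebo at 225 and 675 mg.

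Population is a second, smaller matter. Only cohort 9 can include ages 66 to 70, BMI above 32 or controlled diabetes. Protocol 5.3 monitors fasting glucose because low Lp(a) has been associated with type 2 diabetes, though it also says the evidence does not suggest a causal link. Any diabetic subject on 675 mg would have few or no diabetic counterparts on placebo.

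**Working it through.** **1. The plan's own figures.** The plan gives no figure for this comparison. Its sample-size statements use P(at least one event) = 1 − (1 − p)^n and reproduce from Table 1:
- n = 6, p = 0.20: 1 − 0.8^6 = 73.8% (stated 74%)
- n = 10, p = 0.20: 1 − 0.8^10 = 89.3% (stated 89%)
- n = 60 (active subjects summed from Table 1: 5×6 + 2×9 + 2×6), p = 0.05: 1 − 0.95^60 = 95.4% (stated 95%)

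**2. Size and follow-up of the pool.**
- Placebo subjects, cohorts 6 to 9: 3 + 3 + 2 + 2 = 10
- With the shorter window: 3 + 3 = 6 of 10, by 365 − 225 = 140 days
- Subject-days: 6×225 + 4×365 = 2810, a mean of 281. Ten subjects followed to day 365 would give 3650, so the pool has 2810/3650 = 77% of that.

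The later follow-up of cohorts 6 and 7 does not restore the missing time. It applies only when Lp(a) is still below 80% of baseline, covers Lp(a) and serious events only, and is tabulated separately.

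**3. Effect on crude incidence.** Assume a constant hazard, no drug effect and no dropout. Let p225 be the incidence by day 225. Then
- p365 = 1 − (1 − p225)^(365/225)
- expected pool incidence = 0.6·p225 + 0.4·p365
- cohorts 8 and 9 minus pool = 0.6·(p365 − p225)
- cohorts 6 and 7 minus pool = −0.4·(p365 − p225)

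| p225 | p365 | Pool | Cohorts 8–9 minus pool | Cohorts 6–7 minus pool |
|---|---|---|---|---|
| 20% | 30.4% | 24.1% | +6.2 points | −4.1 points |
| 40% | 56.3% | 46.5% | +9.8 points | −6.5 points |
| 60% | 77.4% | 67.0% | +10.4 points | −7.0 points |

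For a rarer event, p225 = 5% gives p365 = 8.0% and a gap of 0.6×3.0 = 1.8 points.

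**4. Which outputs are touched.** Cumulative TEAE incidence is affected, and so are any maximum or minimum shift tables, because more time and more samples give more extreme values. By-visit laboratory and vital-sign summaries are aligned by study day and are not affected in this way. After day 225, though, only the 4 placebo subjects of cohorts 8 and 9 still have scheduled treatment-period visits. SAP 9.6.5 leaves cohorts 6 and 7 out of the ECG summaries, so the ECG comparison in high-Lp(a) subjects already has equal windows.

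**5. Population.** Of the 10 planned placebo subjects, 3 + 3 + 2 = 8 belong to cohorts 6 to 8 and were recruited under the narrower limits. The other 2 are in cohort 9. The amendment history shows that cohort 9 was added in Amendment 5 and widened only in the latest amendment, so even those 2 could have entered under the narrower limits. Hence at most 2 of 10.

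**6. The synopsis rule.** Pooling all cohorts would give 20 placebo subjects: 4 followed to day 113, 12 to day 225 and 4 to day 365. That is 452 + 2700 + 1460 = 4612 subject-days, a mean of 230.6, against two pools of 10 under Section 13.5.1 and the SAP.

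**The case against.** The best defence is that the study is descriptive. No test or formal contrast of cohort 9 with placebo is planned, and with 6 active and 10 placebo subjects one subject is worth 16.7 or 10 points. A gap of 6 to 10 points is therefore about one placebo subject or less. The constant hazard is also an assumption: after a single dose, events and visits may cluster early, which would shrink the gap. Both points stand and keep this a minor matter. They do not change the direction of the tilt, and nothing planned corrects it.

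The SAP also offers some protection on population. Section 9.4 tabulates demographics, BMI and selected medical history by cohort, and Section 8.4 requires baseline imbalance to be noted in the study report. That would disclose an imbalance but would leave the summaries unchanged.

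Three stronger readings are tempting, and the documents do not support them.
- A reader might infer that only two of the ten placebo subjects would qualify for cohort 9. The limits for cohorts 6 to 8 on age, BMI and diabetes lie inside those for cohort 9, so all ten would satisfy these three. The difference is in who could not have been recruited.
- A reader might infer that the glucose comparison is confounded by diabetes and observation time. Diabetes is permitted in cohort 9, but nothing shows that a diabetic subject was enrolled, and by-visit glucose is aligned by day.
- A reader might infer from the synopsis that the comparator is unsettled for every table. The synopsis refers to Section 13 for the full methods, and Section 13.5.1 and the SAP agree. The conflict is editorial.

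**Conclusion.** The concern holds for cumulative TEAE incidence and for any maximum or minimum laboratory shift tables. Followed as written, the SAP sets cohorts 8 and 9, observed for 365 days, beside a pool in which 6 of 10 planned subjects are observed for 225. The expected distortion is about 6 to 10 points against cohorts 8 and 9, and about 4 to 7 points in favour of cohorts 6 and 7, for true incidence of 20 to 60% by day 225. For uncommon events it is smaller. These sizes rest on a constant hazard, no drug effect, complete follow-up and the planned counts. Protocol 6.4 allows replacements and Protocol 8.1 allows extra subjects in cohort 9, so actual counts may differ.

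The population difference is a limit on interpretation, not a demonstrated bias. The synopsis sentence is wrong as it stands and needs no assumption to correct. Overall this is a worthwhile improvement rather than a flaw that undermines the study.

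**What to change.** - **SAP 9.1 and 9.6.1:** keep the cohort 6 to 9 pool. Add, for cohorts 6 to 9, a TEAE incidence table cut at the day 225 visit (or study exit if earlier) for every subject. All four cohorts have that visit, so windows match and all 10 placebo subjects are kept.
- **Full 365-day window:** add a placebo column limited to cohorts 8 and 9. It has only 4 planned subjects, so it is imprecise. Two of them come from cohort 8, so it does not resolve the population mix.
- **Glucose listings:** show cohort and baseline diabetes status for each subject, so that a diabetic subject in cohort 9 can be read in context.
- **Protocol synopsis, Statistical Considerations:** change the pooling sentence to match Section 13.5.1 and the SAP.

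The cost is one table, one column, two listing variables and one corrected sentence. No new data are needed.
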